#### Hierarchical Testing

This following preplanned hierarchical testing will not be performed due to lack of efficacy per the futility analysis.

Only when OS is significant, the Hochberg procedure will be used to test the secondary endpoints at the overall (two-sided) significance level 0.05: testing will begin with p value  $P_{(m)}$  with corresponding hypothesis  $H_{(m)}$ , where  $P_{(m)}$  is the largest ordered p values amongst 'm' secondary endpoints and  $H_{(m)}$  is the corresponding hypothesis. If  $P_{(m)} \leq \alpha$ , then all hypotheses are rejected. If not, then  $P_{(m-1)}$ , the (m-1)th largest p-value, is compared with  $\alpha/(m-1)$ . If smaller, then all hypotheses from  $H_{(m-1)}$  to  $H_{(1)}$  are rejected. The testing procedure continues in this manner until no significant result is found

**2.2.8.2. Primary Endpoint: Overall Survival**

*Overall survival* (OS) is defined as the time between the randomization and death. Subjects who die, regardless of the cause of death, will be considered to have had an event. All subjects who are lost to the follow-up prior to the end of the trial or who are withdrawn from the trial will be censored at the time of last contact. Subjects who are still being treated will be censored at the last available date where the subject is known to be alive.

OS will be compared between treatment arms using an unstratified two-sided log-rank test as primary analysis. The Kaplan-Meier method will be used to estimate the distribution functions of OS for each treatment arm. The number of events, subjects censored, the estimate of medians and 95% confidence interval for the medians will be presented. The plots of OS using the Kaplan-Meier method will be presented.

Six-month and one-year survival rates will be calculated using the Kaplan-Meier method. The unstratified Cox proportional hazards model will be used to obtain the HR and its 95% CI.

OS will also be compared between treatment arms by a two-sided log-rank test, stratified for the stratification factors: the time from the last dose of first-line platinum therapy to disease progression (6 to 12 months vs >12 to 24 months vs >24 months), Eastern Cooperative Oncology Group (ECOG) performance status score (0 vs 1), BRCA 1/2 status (mutation vs. no mutation) and prior pegylated liposomal doxorubicin therapy (no vs yes).

In case an imbalance in baseline prognostic factors is observed, especially PFI (platinum-free interval: the time from the last dose of first-line platinum therapy to disease progression), a Cox proportional hazards model will also be used to compare 2 treatment arms. The following baseline information includes as covariates: baseline ECOG ("0" vs. "1"), PFI (as continuous), BRCA1/2 status (mutation vs. no mutation), prior pegylated liposomal doxorubicin therapy (no vs yes), and any imbalanced factors. From the Cox proportional hazards regression, HR estimates and their 95% CIs will be estimated for treatment and for the prognostic factors.

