**Figure 1: Kaplan-Meier Plot of Progression-Free Survival**  
(Study ET743-OVA-301: Independent Radiologist Review)

Median survival was 22.2 months for the trabectedin+DOXIL arm and 18.9 months for the DOXIL arm, a 3.3 month improvement with the combination treatment. The HR was 0.86 with 95% CI: 0.72 to 1.02, and a p-value of 0.0835 (un-stratified log-rank test) (Figure 2). An unexpected but significant imbalance in PFI favoring the DOXIL arm (mean PFI: DOXIL=13.3 months; trabectedin+DOXIL=10.6 months) was identified. On the basis of this finding, a retrospective analysis adjusting for the PFI imbalance and other prognostic factors suggested an improvement in OS associated with the trabectedin+DOXIL arm (HR=0.82; 95% CI: 0.69 to 0.98; p=0.0285).

[figure not shown]

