**3. STUDY DESIGN AND RATIONALE****3.1. Overview of Study Design**

This is a randomized, open-label, active-controlled, multicenter study designed to assess the efficacy and safety of trabectedin+DOXIL as a third-line chemotherapy in subjects with platinum-sensitive advanced-relapsed epithelial ovarian, primary peritoneal, or fallopian tube cancer who received 2 previous lines of platinum-based chemotherapy. Approximately 670 adult subjects will be enrolled in this study, with 335 subjects per planned treatment group. At randomization, subjects will be stratified by 4 criteria: 1) the time from the last dose of first-line platinum therapy to disease progression (6 months to 12 months vs >12 months to 24 months vs >24 months), 2) Eastern Cooperative Oncology Group (ECOG) performance status grade (0 vs 1), 3) BRCA 1/2 status (mutation vs no mutation), and 4) prior DOXIL therapy (no vs yes). Subjects will then be randomly assigned in a 1:1 ratio to the trabectedin+DOXIL combination therapy group (Arm A) or to the DOXIL monotherapy group (Arm B).

During the treatment phase, subjects will receive study drug by IV infusion on Day 1 of a 21-day cycle in Arm A and on Day 1 of a 28-day cycle in Arm B. Treatment will continue until the occurrence of disease progression or unacceptable treatment toxicity, or until 2 cycles after assessment of a complete response (CR). Subjects assigned to the trabectedin+DOXIL group (Arm A) will be pretreated with 20 mg of dexamethasone IV, or an equivalent IV corticosteroid, approximately 30 minutes prior to initiation of infusion of DOXIL on Day 1 of each treatment cycle.

Subjects will be followed for survival at least every 8 weeks for the first 2 years after the treatment termination visit and approximately every 12 weeks thereafter. This study will end 2 months after the last subject has received the last dose of study drug, when 514 deaths have been observed, or until the clinical cutoff date.

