### Treatment Allocation

#### *Procedures for Stratification and Randomization*

Prior to randomization, inclusion criteria #4 through #8 must be reviewed by sponsor's medical monitor (Section 4.1, Inclusion Criteria). Following sponsor review, subjects will be stratified by the time from the last dose of first-line platinum therapy to disease progression (6 months to 12 months vs >12 months to 24 months vs >24 months), ECOG performance status grade (0 vs 1), BRCA 1/2 status (mutation vs no mutation), and prior DOXIL therapy (no vs yes). Central randomization will be implemented in this study. Randomization of subjects should occur as close in time as possible before administration of the first dose of study drug(s) and must occur within 7 days of the subject receiving the first dose of study treatment. This maximum 7-day window is given to allow time for provision of central venous access for those subjects assigned to Treatment Arm A (Section 6, Dosage and Administration). Subjects will be randomly assigned, in a 1:1 ratio, to 1 of 2 treatment groups based on a computer-generated randomization schedule prepared before the study by or under the supervision of the sponsor. The interactive voice response system (IVRS) and/or interactive web response system (IWRS)

will assign a unique treatment code, which will dictate the treatment assignment and matching study drug kit for the subject. The requestor must use his or her own user identification and personal identification number when contacting the IVRS/IWRS, and will then give the relevant subject details to uniquely identify the subject.

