### 11.3. Efficacy Analyses

All efficacy endpoints will be analyzed using the All Randomized set of the population. The Kaplan-Meier product limit method and un-stratified Cox proportional hazards model will be used to estimate the time-to-event variables and to obtain the HR and their 95% CI. The un-stratified log-rank test will be used as the primary analysis for treatment comparison. The response rate variables will be evaluated using Chi-square statistic (un-stratified).

Sensitivity analyses for the primary endpoint using the stratified log-rank test will also be performed. Subgroup analyses will be carried out to assess if the treatment effect is consistent across clinically relevant subgroups.

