The retrospective analysis of OS data in Study ET743-OVA-301 indicates that the lack of statistical significance for OS resulted from an imbalance in prognostic factors (PFI) at randomization. BRCA 1/2 mutation status is a key prognostic factor in ovarian cancer. Therefore, subjects in this study will be stratified by BRCA 1/2 mutation status (mutation vs no mutation). The mutation status will only be used to stratify the subjects to treatment (trabectedin+DOXIL or DOXIL). Depending upon the region, it is expected that as many as 50% of potential subjects will have a known BRCA 1/2 status, as this testing is routinely used in standard medical practice to assess genetic risk to specific cancers. For those subjects without a known BRCA 1/2 status, genetic analysis of BRCA 1/2 will be required and, therefore, performed as a study-related procedure. The results of this analysis will be reported to the investigator.

All participating subjects will receive full supportive care and will be followed closely for safety and efficacy throughout the trial. Efficacy assessments will occur according to the internationally accepted response criteria. Safety assessments will occur through regular clinic visits including laboratory analyses. It is anticipated that the volumes of blood drawn for each subject for routine laboratory evaluations throughout the study will be approximately 15 mL for screening serum chemistry and hematology tests; 10 mL for BRCA 1/2 testing at screening (for subjects who do not have a known BRCA 1/2 status); 4 mL for subjects consenting to the optional pharmacogenomics component of the study (where local regulations permit); 45 mL and 60 mL for treatment Arms A and B, respectively, per cycle for serum biochemistry and hematology tests; 4 mL per scheduled CA-125 sample; and 24 mL from those subjects who provide PK samples. Overall, the volume of blood to be drawn is deemed reasonable over the time frame of the study. An IDMC will follow safety and efficacy during the study at regular intervals (approximately every 6 months) and in the prespecified interim analysis, respectively.

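### The primary OS test and hazard ratio leave out the four stratification factors; this costs efficiency but not validity, and a Cox model with the four factors as main effects would recover it

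*SAP*

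**What the plan says.** Protocol 3.1 states that "subjects will be stratified by 4 criteria" and then "randomly assigned in a 1:1 ratio". Protocol 5 repeats the first factor, "Following sponsor review, subjects will be stratified by the time from the last dose of first-line platinum therapy to disease progression", in three bands, and adds ECOG (0 or 1), BRCA 1/2 (mutation or none) and prior DOXIL (no or yes). That makes 3 x 2 x 2 x 2 = 24 cells.

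The documents regard these factors as prognostic:
- Protocol 16.1 says "BRCA 1/2 mutation status is a key prognostic factor in ovarian cancer" and names PFI as the prognostic factor whose imbalance explains the earlier Phase 3 trial's non-significant OS result.
- All four are covariates in a further Cox model (Protocol 11.3, SAP 2.2.8.2), which describes its terms as prognostic factors.

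The deciding test uses none of them. Protocol 11.3 says "The un-stratified log-rank test will be used as the primary analysis for treatment comparison", and SAP 2.2.8.2 agrees: "OS will be compared between treatment arms using an unstratified two-sided log-rank test as primary analysis". The HR and its CI come from an unstratified Cox model. The stratified test is supportive: "Sensitivity analyses for the primary endpoint using the stratified log-rank test will also be performed". The covariate-adjusted Cox model runs only if a baseline imbalance is observed, and it takes PFI as continuous. No reason is given for leaving the factors out of the primary test. (SAP 2.2.1 calls the test one-sided; that is a separate inconsistency, and the test is unstratified there too.)

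**The concern.** If the factors predict survival, stratified randomisation makes the arms more alike than simple randomisation would. An unstratified log-rank test does not account for that, so it becomes conservative. It also estimates a marginal HR, which lies closer to 1 than the HR within strata. An analysis that uses the factors avoids both effects without one more patient. The existing supportive analyses do not close the gap. Neither makes the primary decision, and the adjusted model is triggered by imbalance, whereas this loss arises when the arms are balanced.

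**Working it through.** **1. The plan's own figure.** Inputs from SAP 1.3: HR 0.78, 80% power, two-sided 0.05, 514 deaths, 1:1 allocation. (1.960 + 0.842)² = 7.849.
- Freedman: 7.849 x (1.78/0.22)² = 7.849 x 65.46 = 514 deaths.
- Schoenfeld: 4 x 7.849/(ln 0.78)² = 509 deaths.
- Power at 514 deaths: Φ(√514/2 x 0.2485 - 1.96) = Φ(0.857) = 80.4%, or 80.1% with the O'Brien-Fleming interim at 308.

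The design figure reproduces. The formulas contain no stratification term, so this is the power of the unstratified test at a marginal HR of 0.78.

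**2. Assumptions the documents do not supply.** Prevalences: PFI bands 40/35/25%, ECOG 1 40%, BRCA mutation 25%, prior DOXIL 20%. Two sets of prognostic HRs (PFI 6-12 / >12-24 / >24 months; ECOG 1; BRCA mutation; prior DOXIL):
- Set A weak: 1.3/1.15/1; 1.2; 0.85; 1.1.
- Set A moderate: 1.7/1.3/1; 1.5; 0.7; 1.2.
- Set A strong: 2.2/1.5/1; 1.9; 0.6; 1.4.
- Set B is given as log-HRs for the two longer PFI bands, ECOG 1, BRCA mutation and prior DOXIL. Moderate: -0.3/-0.6; 0.45; -0.45; 0.2. Strong: -0.5/-1.0; 0.65; -0.65; 0.35.

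**3. Simulation.** Permuted blocks of 4 within 24 cells, exponential survival with a 16-month control median, 13 subjects per month, no dropout. N is 670 at 514 deaths and is capped at 580 (assumed) at 232 deaths, the 45% look in SAP 2.2.2.1. Each test has a single look at |Z| > 1.96, with 4,000 trials per cell. The Monte Carlo standard error is up to 0.8 points for power and about 0.3 for alpha.

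Power (%) at within-stratum HR 0.78, and alpha (%) at HR 1:

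| Effects | 514 deaths: unstratified / 24-cell log-rank / Cox | 232 deaths: unstratified / 24-cell log-rank / Cox | Alpha at 514: unstratified / Cox |
|---|---|---|---|
| None | 80 / 78 / 81 | 48 / 45 / 48 | 5.1 / 5.0 |
| A weak | 80 / 78 / 81 | 47 / 44 / 47 | 5.6 / 5.8 |
| A moderate | 76 / 79 / 81 | 44 / 43 / 47 | 3.6 / 4.7 |
| B moderate | 74 / 77 / 80 | 45 / 46 / 49 | 3.9 / 5.2 |
| A strong | 72 / 78 / 81 | 39 / 43 / 47 | 2.8 / 4.3 |
| B strong | 67 / 77 / 80 | 37 / 43 / 47 | 2.7 / 4.6 |

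Before rounding, Cox minus unstratified is 4.6 to 13.0 points at 514 deaths under moderate or strong effects, and 3.4 to 9.3 at 232. A further run of 1,500 trials per setting, also on assumed effects, gave 74 versus 79% and 66 versus 80% at 514 deaths, so I quote 5 to 14. At 270 deaths, a count not in the documents, the gap was about 5 to 10.

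**4. Where the loss comes from.** With a within-stratum HR of 0.78, the average unstratified HR at 514 deaths was 0.79 to 0.80 (moderate) and 0.80 to 0.81 (strong). The step 1 power formula gives 76% at 0.79, 72% at 0.80 and 67% at 0.81, close to the unstratified column. With the marginal HR itself set near 0.78, a 2,500-trial run gave 82 versus 85% (moderate) and 83 versus 91% (strong). The planned test then keeps its 80%, and the adjusted test still does better.

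**5. The 24-cell log-rank.** Sparse cells cost it about 6% of the information. Across runs at 514 deaths it loses about 1 to 3 points when effects are absent or weak. At 232 deaths about 9 to 10 of the 24 cells hold fewer than 5 deaths.

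**The case against.** The strongest reply is that this is a preference. Protocol and SAP agree on the primary test, alpha is protected, a four-factor stratified log-rank is already prespecified unconditionally, and 80% is the right power for the marginal HR the design assumed. All of that stands, and it limits the point to efficiency.

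A reader might infer more than the documents support:
- **That the design delivers less than its stated 80%.** It does so only if 0.78 is read as a within-stratum HR. The sample-size text assumes one constant hazard per arm, which fits the marginal reading, and no stratification gain was built into the 514.
- **That the earlier trial measures the loss.** Protocol 1.2.1 says "a retrospective analysis adjusting for the PFI imbalance and other prognostic factors suggested an improvement in OS", with the HR moving from 0.86 to 0.82. That adjustment corrected a chance imbalance (mean PFI 13.3 versus 10.6 months, favouring DOXIL), which stratifying on PFI largely prevents here. It is not a measure of the efficiency an unstratified test gives up.

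Two further objections keep some force. The simulated survival times follow the same main-effects model that was then fitted, so the Cox results are for favourable conditions. And replacing the primary test after HR 0.962 is known is a post-hoc change, not a wording edit. At 232 deaths that HR gives Z = √232/2 x ln 0.962 = -0.30, so a gain of a few points of power would not plausibly change the conclusion.

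**Conclusion.** The point holds as an efficiency loss. The plan randomises on four factors it treats as prognostic and then omits them from the test and HR that decide OS, without giving a reason. Under assumed moderate to strong effects the cost against a four-factor Cox model is about 5 to 14 points of power at 514 deaths and 3 to 9 at 232, with alpha near 3-4% at 514 deaths instead of 5%. If the effects are weak or absent, the cost is about nil and the Cox test loses nothing measurable. These sizes rest on prevalences and prognostic strengths the documents do not give, on a within-stratum HR of 0.78 and on a correctly specified model. Nothing here shows an invalid test, a misstated power or a different outcome for the trial.

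**What to change.** In SAP 2.2.8.2 and Protocol 11.3, take the primary OS treatment test, HR and 95% CI from a Cox model with PFI category (as randomised), ECOG, BRCA 1/2 and prior DOXIL as prespecified main effects, fitted regardless of observed imbalance. Keep the unstratified and the stratified log-rank tests as sensitivity analyses. Do not promote the 24-cell stratified log-rank to primary, because of the sparse cells.

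For the 18 January 2018 analysis, label the change as made after the futility result and report it beside the prespecified unstratified result. If the sponsor prefers to leave the primary test alone at this stage, the minimum is to state why it is unstratified and to run the four-factor Cox model unconditionally as a supportive analysis.

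Costs: the HR becomes conditional on the factors, so it is not directly comparable with a marginal HR; the result relies on proportional hazards and on the form of the covariate terms; and the change carries the post-hoc label. No additional patients or data are needed, since all four factors must be known before randomisation.

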**Subgroup analyses**

The following preplanned subgroup analysis will not be performed due to lack of efficacy per the futility analysis.

YONDELIS®: Statistical Analysis Plan Study ET743-OVC-3006

Subgroup analysis is planned for the primary endpoints OS to investigate whether treatment effects are consistent within subgroups. Each subgroup will be analyzed separately. The subgroups are as follows:

- Age (<65, ≥65)
- PFI (6 to 12 months vs >12 to 24 months vs >24 months),
- ECOG performance status score (0 vs 1),
- BRCA 1/2 status (mutation vs. no mutation)
- prior pegylated liposomal doxorubicin therapy (no vs yes)

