### **11.5. Patient Reported Outcomes**

Patient reported outcome assessments based on the EQ-5D-5L and QLQ-OV28 questionnaires will be analyzed to determine if therapeutic response and/or side effects of therapy are accompanied by measurable changes in the PROs. The analysis will be performed on summary scores as well as subscales, and individual symptoms, with specific analytical methods outlined in a formal Statistical Analysis Plan developed prior to database lock.

Differences between the treatment arms will be evaluated using published methods. Specific interest centers on abdominal and gastrointestinal symptom scales of QLQ-OV28. The change in PRO scores between baseline and each postbaseline assessment will be described overall and according to the response to treatment.

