### **2.1.3.3. Definition of Subgroup**

In addition to the main analysis, the efficacy analysis will be performed by the levels of stratification factors.

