##### **2.2.8.8. Patient Reported Outcomes**

The following preplanned patient reported outcome analysis will not be performed due to lack of efficacy per the futility analysis.

The Patient Reported Outcomes will be measured by the OV28 and the EQ-5D questionnaires. Patients will be requested to fill these out at baseline, at the end of every cycle, at the treatment termination visit, and every 8 weeks till start of subsequent treatment. The analyses of these data will be performed on summary scores as well as subscales, and individual symptoms.

YONDELIS®: Statistical Analysis Plan Study ET743-OVC-3006

Change from baseline at each time point and treatment termination will be analysed for selected scales of the OV28 items. In particular, Abdominal/Gastrointestinal Symptoms scales of OV28 will be tested based on the grouping criteria as specified in Greimel et al. Mean score changes from baseline at each time point and treatment termination will be compared between the treatment arms using T-test. The changes will also be analyzed using model for longitudinal data, taking the potential missing data and dropout into account.

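### The SAP cancels OS subgroups and all PRO analysis on futility grounds, although neither depended on significant OS and other current text still calls for both

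*SAP*

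**What the plan says.** **Subgroups.** SAP 2.1.3.3 states: "In addition to the main analysis, the efficacy analysis will be performed by the levels of stratification factors". SAP 2.2.8.2, under Subgroup analyses, then states: "The following preplanned subgroup analysis will not be performed due to lack of efficacy per the futility analysis". The cancelled list is age, PFI, ECOG, BRCA 1/2 status and prior pegylated liposomal doxorubicin, and it concerns OS only. Protocol 11.3, current as of Amendment 6, states: "Subgroup analyses will be carried out to assess if the treatment effect is consistent across clinically relevant subgroups". It names no endpoint and sets no condition.

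**PROs.** SAP 2.2.8.8 states: "The following preplanned patient reported outcome analysis will not be performed due to lack of efficacy per the futility analysis". Evaluating PROs remains an exploratory objective in Protocol 2.1 and SAP 1.1. Protocol 11.5 still plans the analysis and leaves its methods to the SAP: "with specific analytical methods outlined in a formal Statistical Analysis Plan developed prior to database lock". It also says that differences between arms will be evaluated, and that "The change in PRO scores between baseline and each postbaseline assessment will be described overall and according to the response to treatment". The Amendment 6 Time and Events Schedule keeps QLQ-OV28 and EQ-5D-5L at the termination visit.

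**What depended on OS.** In both documents (Protocol 11.3 and SAP 2.2.8.1.1, each under Hierarchical Testing), only the Hochberg procedure for the secondary endpoints is conditional on significant OS. The SAP cancels that too.

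**The concern.** For OS by stratification factor, the SAP has one sentence that requires the analysis and another that withdraws it, with no link between them. Two programmers could deliver different outputs, each with SAP text in support. The PRO objective is left with no result at all.

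The stated reason, lack of efficacy at the futility look, fits a testing hierarchy that could open only after significant OS. It does not explain dropping a description of consistency or of patient experience. Protocol 11.5 gives the PRO analysis the purpose of showing whether side effects, as well as response, go with measurable PRO change. The IDMC recommendation to stop rested partly on higher toxicity in Arm A, so that question outlives the futility result. PFI matters too: the rationale in Protocol 1.2.1 relies on a PFI subgroup of the earlier Phase 3 study (OS HR 0.64 for 6 to 12 months). The overall HR and the stratified log-rank test do not show OS within PFI levels.

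**Working it through.** **1. Overlap of the two subgroup texts.**

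| Cancelled OS subgroup (SAP 2.2.8.2) | Stratification factor (SAP 1.2), so covered by SAP 2.1.3.3? |
|---|---|
| PFI, three levels | Yes |
| ECOG 0 vs 1 | Yes |
| BRCA 1/2 status | Yes |
| Prior pegylated liposomal doxorubicin | Yes |
| Age <65 vs ≥65 | No |

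The overlap is four of five, for OS only. PFS and ORR by stratification factor are not cancelled anywhere and remain planned under SAP 2.1.3.3.

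**2. How precise OS subgroups could be.** The documents do not give the number of deaths at the 18 January 2018 cutoff. I assume the 232 that the SAP gives for the second futility look (0.45 × 514 = 231.3), split evenly between arms, so that the variance of ln(HR) is 4/D. This approximation reproduces the SAP's own stopping probabilities at HR ≥ 0.93:

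- Under the null: z = ln(0.93) × √232 / 2 = −0.553, so P(stop) = 71.0% (SAP: about 71%).
- Under HR 0.78: z = ln(0.93/0.78) × √232 / 2 = 1.340, so P(stop) = 9.0% (SAP: about 9%).

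For a subgroup holding a fraction f of the deaths, CI = exp(ln 0.962 ± 1.96 × 2 / √(f × 232)). The fractions are assumed, and every subgroup is centred on the overall HR.

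| f | Deaths | 95% CI |
|---|---|---|
| 0.2 | 46.4 | 0.54 to 1.71 |
| 0.5 | 116 | 0.67 to 1.38 |
| 0.8 | 185.6 | 0.72 to 1.28 |
| 1.0 | 232 | 0.74 to 1.24 |

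**3. Whether the cancelled PRO text could simply be restored.** It could not, for three reasons.

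- *Timing.* SAP 2.2.8.8 says "Patients will be requested to fill these out at baseline, at the end of every cycle, at the treatment termination visit", then every 8 weeks for both instruments. Protocol 9.1.3.5 has Day 1 of each cycle and end of treatment, with only EQ-5D-5L about every 8 weeks afterwards.
- *Tests.* "Mean score changes from baseline at each time point and treatment termination will be compared between the treatment arms using T-test". That is one unadjusted comparison per time point, with no allowance for dropout. The same section also names a longitudinal model that does allow for missing data and dropout.
- *Time scale.* Without delays, Day 1 of cycle n falls at week 3(n − 1) in Arm A and week 4(n − 1) in Arm B. Cycle 5 Day 1 is therefore week 12 in Arm A and week 16 in Arm B. The schedules coincide at week 12 (Cycle 5 in A, Cycle 4 in B) and week 24 (Cycle 9 and Cycle 7), but only without delays. Protocol 6 allows a +2 day window, Protocol 6.1 allows up to 3 weeks of delay, and SAP 2.1.1 lengthens the cycle accordingly. Matching on exact weeks would fail, so analysis windows are needed.

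**The case against.** The best defence is that these are open decisions. Both SAP sections call the analyses preplanned, say they will not be done and give the reason. SAP 2.1.3.3 is one general sentence that names no endpoint. The subgroup section is specific to OS, so it may be taken to govern OS while the general sentence survives for PFS and ORR. Protocol 11 describes itself as general and leaves details to the SAP. A sponsor may judge consistency moot when there is no overall effect. PROs are exploratory, subgroup intervals will be wide, and the overall OS analysis, the stratified log-rank test and a covariate-adjusted Cox model (if imbalance is seen) all remain.

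Much of this stands. A reader might infer that the SAP gives flatly opposite instructions on OS; that is too strong, because specific over general is a fair reading, though one the SAP never states. A reader might also infer that a complete PRO dataset is in hand and unused. The documents show scheduled collection only: they give no completion rates, and Protocol 9.1.4 ends follow-up data collection with Amendment 6. Nor do they support dropping all between-arm PRO evaluation, since Protocol 11.5 says arm differences will be evaluated.

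What the defence does not do is reconcile SAP 2.1.3.3, Protocol 11.3 or Protocol 11.5 with the cancellations. Imprecision is a sound reason to keep subgroup results descriptive, but it is not the reason the SAP gives for omitting them.

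**Conclusion.** The concern holds as a should-fix point. Four of the five cancelled OS subgroups are still covered by an unconditional SAP sentence, the protocol's subgroup promise is unamended, and one retained exploratory objective has no analysis. The futility reason matches only the Hochberg testing.

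The consequence is limited. No primary or secondary conclusion changes. OS subgroup results could only be descriptive, with intervals between about 0.54 to 1.71 and 0.72 to 1.28 for subgroups holding 20% to 80% of deaths. Those figures rest on an assumed 232 deaths, an even split between arms and assumed shares. It should not be inferred that subgroup results could overturn the futility finding; intervals of this width cannot carry such a claim. Where and how the BRCA analysis of Protocol 11.6 is reported is a separate matter and not part of this point.

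**What to change.** 1. **SAP 2.2.8.2, Subgroup analyses.** Replace the cancellation with descriptive OS hazard ratios and 95% CIs for the five listed subgroups, without p-values or significance claims. Cross-reference SAP 2.1.3.3 and state that it continues to cover PFS and ORR by stratification factor.
2. **SAP 2.2.8.8.** Replace the cancellation with a descriptive summary of change from baseline in whatever PRO data were collected up to 18 January 2018. Centre it on the QLQ-OV28 abdominal/gastrointestinal scales, by arm and by response as in Protocol 11.5. Report completion counts. Use the collection times of Protocol 9.1.3.5 and compare arms in defined calendar-time windows, not by cycle number.
3. **Between-arm PRO evaluation.** Drop the repeated t-tests. Keep the longitudinal model already named in SAP 2.2.8.8 as an exploratory between-arm estimate with its CI. This meets Protocol 11.5 and addresses dropout.
4. **Record.** List any analysis still dropped as a change from the protocol plan made after the futility result. Keep the Hochberg testing cancelled.

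The cost is one forest plot, a cross-reference, questionnaire scoring, a small set of PRO tables and one model. The downside is imprecise estimates that must be labelled descriptive, and some PRO programming in a stopped trial.
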